5. STUDY DRUG ADMINISTRATION AND MANAGEMENT

Study drug refers to DCC-2618 and matching placebo.

5.1. Study Drug Description

DCC-2618 will be supplied as 50 mg strength tablets for oral administration. The tablets contain the active pharmaceutical ingredient formulated as a % w/w on a hydroxypropyl methylcellulose acetate succinate. Other excipients include microcrystalline cellulose, lactose, cross-linked polyvinylpyrrolidone, fumed silica, and magnesium stearate.

Placebo will be supplied as identically sized and color-matched tablets.

5.2. Study Drug Dose and Administration

Study drug may be dispensed only under the supervision of the Investigator or an authorized designee and only for administration to study patients. Patients will be randomized to receive 150 mg QD of DCC-2618 or placebo in repeated 28-day cycles.

The Investigator or designee must instruct the patient to take the study drug as per protocol.

- Patients should be instructed to take their assigned dose at the same time each day.
- Patients should take their study drug dose with a 6-ounce glass of water with or without food.
- Patients must be instructed to swallow the tablets whole. Tablets must not be crushed, chewed, or dissolved in liquid or food.
- The date, amount taken, and time of study drug administration must be recorded for the 3 days prior to PK sample collections and on the days of PK sample collection.
- On days of scheduled visits, the dose of study drug must be administered at the site after pre-dose assessments have been completed. The date, amount taken and time of study drug administration must be recorded.

If a patient dose escalates to 150 mg BID of DCC-2618, the Investigator or designee must instruct the patient to take the study drug as per protocol.

- Patients should be instructed take the study drug twice a day, at least 6 hours apart, and at the same time each day.
- Patients should take their study drug dose with a 6-ounce glass of water with or without food.
- Patients must be instructed to swallow the tablets whole. Tablets must not be crushed, chewed, or dissolved in liquid or food.
- The date, amount taken, and time of study drug administration must be recorded for the 3 days prior to PK sample collections and on the days of PK sample collection.
- On days of scheduled visits, the dose of study drug must be administered at the site after pre-dose assessments have been completed. The date, amount taken and time of study drug administration must be recorded.

If a patient forgets to take a dose at the scheduled time, the patient can take the scheduled dose if taken within 8 hours of the scheduled time that was missed for QD dosing and within 4 hours of the scheduled time that was missed for BID dosing. If more than 8 hours (for QD dosing) or 4 hours (for BID dosing) have passed after the scheduled time, then that missed

dose must be omitted and the patients must continue treatment with the next scheduled dose. On days of planned study visits, patients will be informed to take the study drug at the study site as per the Schedule of Assessments.

If vomiting occurs immediately after taking a dose, that dose must not be “made up,” and the patient may be offered prophylactic anti-emetics prior to their next dose.

For information on overdose, refer to [Section 7.12](#).

5.2.1. Intra-patient Dose Escalation

- Patients who are randomized to DCC-2618 150 mg QD and have disease progression by modified RECIST based on independent radiologic review may continue DCC-2618 at an increased dose of 150 mg BID.
- Patients who are randomized to placebo who cross over to receive DCC-2618 150 mg QD and have disease progression by modified RECIST based on Investigator assessment may continue DCC-2618 at an increased dose of 150 mg BID.

Upon disease progression, patients must be counseled on any other available treatment options. At the time of dose escalation, the patient must return to the site for study drug to be dispensed. Detailed instructions will be provided in the Study Reference Manual.

5.2.2. Crossover

Patients randomized to placebo who have disease progression by modified RECIST based on independent radiologic review will be given the option to cross over to receive DCC-2618 150 mg QD. Once the independent radiologic review has confirmed disease progression, the patient's study drug treatment will be unblinded and either the patient may start the crossover procedures, or discontinue if the patient declines to enter the crossover.

The initiation of crossover will start with the assessments described in Cycle 1 Day 1 of [Table 2](#) (Schedule of Assessments for Crossover). Following crossover, if a patient has disease progression by modified RECIST based on Investigator assessment, then the patient may continue DCC-2618 with the same dose if the Investigator feels the patient is receiving benefit from DCC-2618, may dose escalate according to the rules in [Section 5.2.1](#), or may discontinue DCC-2618. Detailed instructions will be provided in the Study Reference Manual.

5.3. Dose Interruption and Modification

Study drug may be interrupted or modified (ie, dose reduction) at the discretion of the Investigator at any time due to adverse event (AE), to accommodate palliative treatment, or for other reasons after consultation with the Sponsor. An interruption must be limited to no more than 1 cycle (28 days). Upon resumption following a dose interruption, the Investigator must continue with the patient's original visit schedule calculated from Cycle 1 Day 1.

5.3.1. Dose Interruption due to Planned Medical Procedures

For surgeries that occur while the patient is on study, the extent of the procedure and rate of healing following the procedure must be taken into consideration. The following guidance applies:

- Planned minimally invasive surgery: study drug must be interrupted for 3 days prior to and 3 days after surgery.

- Planned major surgeries: study drug must be interrupted for a minimum of 5 days prior to surgery and continuation of study drug must be determined after consultation with the Sponsor.
- Unplanned surgery: study drug must be interrupted immediately and continuation of study drug must be determined after consultation with the Sponsor.

5.3.2. Dose Interruption and Modification Due to Toxicity

Study drug may be interrupted or reduced as described in [Table 7](#) at the discretion of the Investigator at any time due to AEs and according to the guidelines described in [Table 8](#), [Table 9](#), and [Table 10](#). Whenever possible, dose reductions must be prospectively discussed with the Sponsor. If study drug is interrupted and then study drug is restarted, the patient should remain on their original cycle schedule.

If any patient requires a dose lower than 50 mg QD or if a patient has had their dose reduced and has disease progression confirmed by the independent radiologic reviewer, the patient must be discontinued from study drug, the End-of-Treatment (EOT) Visit and Safety Follow up Visit must be conducted, and the patient must be followed for overall survival.

Table 7: Dose Reduction Steps for Study Drug

Starting Dose of Study Drug	1 ST Dose Reduction	2 ND Dose Reduction
150 mg QD	100 mg QD	50 mg QD

Following disease progression by modified RECIST, patients who dose escalate to 150 mg BID and have toxicity must be dose reduced according to the steps outlined in [Table 8](#).

Table 8: Dose Reduction Steps for Patients Who Progressed and Dose Escalated to 150 mg BID

Starting Dose of Study Drug	1 ST Dose Reduction	2 ND Dose Reduction
150 mg BID	100 mg BID	150 mg QD

If the AE returns to Grade 1 or baseline, the patient may be re-escalated. Efforts must be made to re-escalate the patient to the dose level at which the AE occurred. If the dose level is reduced to the 1st dose reduction level and the AE returns to Grade 1 or baseline, the patient may be re-started at the starting dose level. If a patient has two sequential dose reductions and the AE returns to Grade 1 or baseline at the 2nd dose reduction level, the patient may be re-started at the 1st dose reduction level and must remain at this dose level for 1 cycle without interruption before escalating to the starting dose level.

If the AE leading to dose modification does not return to Grade 1 or baseline within 1 cycle (28 days), then the study drug must be discontinued, unless the event is considered not clinically significant by the Investigator, in which case the possibility of restarting the patient at a reduced dose level may be made after consultation with the Sponsor.

Table 9: Dose Modifications for Dermatologic Toxicities and Arthralgia/Myalgia

Toxicity Grade	Dose Modification Guide
Grade 1	Institute support measures and continue the study drug at the current dose
Grade 2	
Institute support measures and continue the study drug at the current dose
 
If no improvement within 7 days, then interrupt the study drug
 
 • If the event returns to Grade 1 or baseline within 7 days, resume the study drug at the same dose level • If the event returns to Grade 1 or baseline after 7 days, resume the study drug at a reduced dose level 
If this is a recurrence, after event returns to Grade 1 or baseline, resume the study drug at a reduced dose level regardless of time to improvement
 
If after a dose reduction the event is maintained at Grade 1 or baseline for at least 1 cycle (28 days) of dosing, consider re-escalating the study drug by 1 dose level

Grade 3	
Institute support measures
 
Interrupt study drug for at least 7 days or until the event returns to Grade 1 or baseline (maximum 28 days)
 
 • Resume study drug at a reduced dose level 
If after a dose reduction the event is maintained at Grade 1 or baseline for at least 1 cycle (28 days) of dosing, consider re-escalating the study drug by 1 dose level

Grade 4	Discontinue study drug unless the event is not considered life-threatening. Patients may continue study drug with non-life threatening events upon discussion with the Sponsor.
Any Grade	
Stevens-Johnson Syndrome:
 
If a patient experiences Stevens-Johnson syndrome (SJS), study drug must be permanently discontinued. The patient should be immediately referred to a hospital for clinical evaluation and supportive care/management per institutional guidelines. Re-administration of study drug is not allowed due to the risk of recurrent SJS. Caution for recurrence of SJS with other similar agents (TKIs for GIST) is advised, as the one patient who has been diagnosed with SJS while being treated with DCC-2618 had a similar reaction while being treated with regorafenib prior to DCC-2618.

Table 10: Dose Modifications and Management of Hypertension

Toxicity Grade	Management Guideline*
Grade 1 Prehypertension (systolic BP 120 - 139 mm Hg or diastolic BP 80 - 89 mm Hg)	Continue BP monitoring Continue the study drug at the current dose level
Grade 2 Systolic BP 140 - 159 mm Hg or diastolic BP 90 - 99 mm Hg Or Symptomatic increase by >20 mm Hg (diastolic) or to >140/90 mm Hg if previously within normal limits	Treat BP to achieve diastolic BP ≤ 90 mmHg and or systolic BP ≤ 140 mmHg 
 • If BP was previously within normal limits, start antihypertensive monotherapy • If patient is already on antihypertensive medication, titrate dose up Continue the study drug at the current dose level Hold study drug if symptomatic increase by 20 mmHg (diastolic BP) until symptoms resolve and diastolic BP ≤ 90 mmHg On resuming study drug, continue at the same dose level
Grade 3 Systolic BP ≥ 160 mm Hg or diastolic BP ≥ 100 mm Hg) Or More than 1 drug or more intensive therapy than previously indicated	Treat to achieve diastolic BP ≤ 90 mmHg and or systolic BP ≤ 140 mmHg 
 • Start antihypertensive medication and/or • Increase current antihypertensive medication and/or • Add additional antihypertensive medication If symptomatic, hold study drug until diastolic BP ≤ 90 mmHg and/or systolic BP ≤ 140 mmHg, and symptoms resolve On resuming study drug, continue at the same dose level If BP is not controlled with addition of a new or more intensive therapy, reduce the study drug by 1 dose level If Grade 3 hypertension recurs despite study drug dose reduction and antihypertensive therapy, reduce the study drug by 1 additional dose level
Grade 4 Life-threatening consequences (eg, malignant hypertension, transient or permanent neurologic deficit, hypertensive crisis)	Treat BP per institutional guidelines Discontinue study drug

BP=blood pressure

*If BP remains controlled for at least 1 full cycle (28 days), study drug dose re-escalation is permitted at the Investigator's discretion.

Table 11: Dose Modifications for Treatment Related Adverse Events Other than Dermatologic Toxicities, Arthralgia/Myalgia, and Hypertension

Toxicity Grade	Management Guideline ¹
Any Grade 3 or 4	Interrupt study drug dosing until event has resolved to Grade 1 or baseline Once the AE returns to Grade 1 or baseline, reduce study drug by 1 dose level If a patient tolerates the reduced dose without recurrence of the event for at least one cycle, consider re-escalating the dose of study drug to the prior dose level
Asymptomatic/Not clinically significant Grade 3 or 4 laboratory AEs (including CPK and lipase) that persist ≤10 days	Closely monitor for clinical symptoms and continue the study drug at the current dose level Repeat labs within 10 days.
Asymptomatic/Not clinically significant Grade 3 or 4 laboratory AEs (including CPK and lipase) that persist >10 days	Closely monitor for clinical symptoms; for Grade 4 events, interrupt study drug until the event returns to Grade 3 
 • Asymptomatic Grade 3 or Grade 4 elevations of plasma enzyme: lipase or CPK do not require dose interruption Once the AE returns to Grade 3, resume the study drug at the current dose level or consider reducing by 1 dose level per Investigator discretion after discussion with the Sponsor.
Clinically Significant Grade 3 or 4 laboratory AEs (including CPK and lipase)	Interrupt study drug. If the Investigator assesses that restarting study drug is in the patient's best interest, the Sponsor must be contacted for discussion and determination if restarting is allowed.

AE=adverse event; CPK=creatine phosphokinase

1. The rules for dose modifications for laboratory AEs will be based on local laboratory results.

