5.10.1. Blinding

The patients and all site personnel, including the Investigator, the site monitor, and the study team must be blinded, with the exception of the following:

- Any site personnel for whom this information is important to ensure the safety of the patient in the event of a life threatening medical emergency
- Any site personnel for whom this information is important to ensure the safety of the patient and their fetus in the event of a pregnancy
- Vendors responsible for pharmacovigilance and regulatory personnel at the Sponsor to satisfy serious adverse event (SAE) processing and reporting regulations
- Clinical Supply Chain
- Unblinded statistician and programmer preparing the final (production) randomization list and unblinded analyses for the independent data monitoring committee (IDMC)
- IDMC
- Vendors analyzing PK and biomarker samples
- Vendor conducting the population PK analysis
- IRT vendor

- The Investigator, patient, site personnel, site monitor and study team will become unblinded to a specific patient's treatment assignment, if the patient has disease progression based on independent radiologic review.

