9.7. Blinding

Prior to the unblinding of study data, the Sponsor will approve a comprehensive statistical analysis plan (SAP).

Where required, safety personnel at the Sponsor or designee may be unblinded to a patient's study drug assignment to meet reporting requirements to regulatory agencies. In addition, the Investigator, patient, Sponsor, and study team will be unblinded at the time the patient has disease progression by modified RECIST based on independent radiology review.

Additional Sponsor representatives may be unblinded to some data for the purposes of ensuring adequacy of study conduct, including proper distribution of study drug.

At no point in time before official full study unblinding will any aggregate efficacy and safety analyses be conducted by the Sponsor or Sponsor representatives, unless there is explicit permission to do so, for instance high level efficacy assessment for the purposes of IDMC review to determine the adequacy of the risk/benefit profile of the drug as it pertains to the conduct of the clinical trial.

Upon determining the results based on the primary PFS analysis, all remaining patients will be unblinded to their treatment assignment and patients assigned to placebo will be allowed to cross-over to active therapy.

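### Protocol 5.3.2 takes any dose-reduced patient off study drug at confirmed progression and does not preserve the crossover that 5.2.2 offers placebo patients on the same trigger

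*Protocol*

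**What the plan says.** Protocol 5.3.2 has one sentence with two triggers: a patient needs less than 50 mg QD, or "a patient has had their dose reduced and has disease progression confirmed by the independent radiologic reviewer, the patient must be discontinued from study drug". Both triggers have the same consequence. Study drug stops, the End-of-Treatment and Safety Follow-up Visits take place, and "the patient must be followed for overall survival". Neither trigger is limited to an arm.

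Section 5 gives the definition: "Study drug refers to DCC-2618 and matching placebo".

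Section 5.2.2 starts from the same event, progression by independent radiologic review (IRR), in a patient randomized to placebo. After unblinding, "either the patient may start the crossover procedures, or discontinue if the patient declines to enter the crossover". Sections 3.1 and 6.10.1, Table 1 footnote 21 and SAP 2.2.2 repeat the offer of DCC-2618 150 mg QD. None makes an exception for a patient whose dose was reduced earlier.

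**The concern.** A placebo patient whose blinded tablets were reduced, and who then has IRR-confirmed progression, meets the conditions of both rules at once. One says stop study drug and go to follow-up; the other says offer DCC-2618.

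What is at stake is an individual patient's access to active drug. Section 1.4.1 presents crossover as the answer to the ethical concern about giving placebo to patients with advanced cancer, and says that no other approved option remains after the three prior agents. A reduction of placebo tablets carries no information about how the patient would tolerate DCC-2618, so it gives no pharmacological reason to withhold it.

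**Working it through.** The conflict is textual, so the check is to set the rules side by side. The plan states no figure to reproduce.

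**Step 1: are placebo patients within the clause?** The clause concerns a patient and study drug. Under Section 5, study drug includes placebo, and no arm is named. Yes.

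**Step 2: can a placebo patient have a dose reduction?** Section 5.3 lets the Investigator reduce study drug for an adverse event, and Tables 9 to 11 call for reductions at given toxicity grades whatever the arm. Section 5.10.1 says "The patients and all site personnel, including the Investigator, the site monitor, and the study team must be blinded", subject to listed exceptions, so the Investigator ordinarily reduces without knowing the assignment. Yes.

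**Step 3: is it the same decision point?**

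| | Protocol 5.3.2 | Protocol 5.2.2 |
|---|---|---|
| Trigger | IRR-confirmed progression after a dose reduction | IRR-confirmed progression |
| Arm | Not limited | Placebo |
| Consequence | Study drug must stop; EOT, safety and survival follow-up | Unblind; crossover, or discontinue if declined |
| Mentions the other rule | No | No |

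Progression after crossover is judged by the Investigator (5.2.2, 6.10.1), not by IRR. The 5.3.2 clause therefore acts at first progression, where crossover is decided. It cannot be explained as a rule for patients who have already crossed over.

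**Step 4: does any text say which rule prevails?** Sections 3.1 and 6.10.1, Table 1 footnote 21 and SAP 2.2.2 restate the offer without an exception. The note under Figure 1 leaves the next step after progression and unblinding to patient choice, which favours crossover but does not mention dose reduction. No text sets an order of precedence.

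**Step 5: does it reach the analysis?** SAP 8.1 counts the first IRR progression, or death, on the initially assigned treatment. The clause is triggered by that progression, so it acts only once the PFS event exists. SAP 8.2 takes ORR from assessments before the PFS event or censoring. OS runs over the whole study (SAP 3.1) and could in principle be touched, but only through the few patients concerned.

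**Step 6: how many patients?** The documents give no dose-reduction rate on placebo, so the count cannot be derived. As an illustration only, take the 35 placebo PFS events planned in Protocol 9.1 as a ceiling and assume that 2.5% to 10% of these patients are reduced before progression:

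- All 35: 35 × 0.025 = 0.9 and 35 × 0.10 = 3.5 patients. Chance of at least one: 1 − 0.975^35 = 0.59 and 1 − 0.90^35 = 0.97.
- Only those progression-free at a first scan at 28 days, exponential with the planned 1-month placebo median: 0.5^(28/30.44) = 0.529, and 35 × 0.529 = 18.5. Then 18.5 × 0.025 = 0.5 and 18.5 × 0.10 = 1.85 patients. Chance of at least one: 1 − (1 − 0.529 × 0.025)^35 = 0.37 and 1 − (1 − 0.529 × 0.10)^35 = 0.85.

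The assumed rates drive every one of these figures. For a given rate they overstate the count, because PFS events include deaths without progression and some patients would decline crossover.

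**The case against.** The best case for the plan is that the two sections can be read together. The crossover offer is specific to placebo patients and is repeated throughout, while 5.3.2 is a general rule in a toxicity section; the specific rule would normally govern. Nothing in the 5.3.2 consequence forbids crossover: survival follow-up applies to every patient, including those on the crossover schedule (Table 2 footnote 3), and crossover opens a new Cycle 1 Day 1. Stopping the blinded tablets, unblinding and then crossing over would satisfy both sections. Once unblinded, a placebo patient is known to have had no DCC-2618 dose to reduce. The Study Reference Manual, to which 5.2.2 defers for detail, may settle the matter, but it is not among the documents.

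This reading is plausible, and it limits the severity. It does not remove the conflict, because 5.3.2 does not state it. DCC-2618 given after crossover is itself study drug under Section 5, and the same sentence gives the same outcome to patients who need less than 50 mg QD, for whom stopping is plainly final.

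A reader might go further than the documents allow in three ways:

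- **Sites would treat identical patients differently.** This is speculation. Unblinding and drug supply run through the interactive response system, and reductions are to be discussed with the Sponsor where possible.
- **Section 9.7 makes the rule perverse**, because at the primary analysis "all remaining patients will be unblinded to their treatment assignment and patients assigned to placebo will be allowed to cross-over to active therapy" with no dose-reduction condition, while a reduced patient who progressed earlier would be refused. With 35 events planned in 35 placebo patients (9.1), almost nobody would be left to benefit, so the contrast is nearly empty.
- **The DCC-2618 arm has the same fault.** There the clause reads as a deliberate exception to the post-progression options. Adding cross-references, or saying whether it covers a patient already back at 150 mg QD, is optional editing and not part of this point.

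**Conclusion.** The point holds as a conflict between two written rules: on its wording, 5.3.2 denies a dose-reduced placebo patient the crossover that 5.2.2 offers on the same event. It is of minor severity. The documents do not show that any patient was or would be refused crossover, and the harmonising reading may well be what the sponsor intended.

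The number affected is unknown and probably few or none; the illustrative counts rest entirely on an assumed reduction rate of 2.5% to 10%. Primary PFS, power and type I error are untouched, and any effect on OS would be small. The case for a change rests on individual access to active drug.

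**What to change.** Limit the progression clause in Protocol 5.3.2 to patients unblinded to DCC-2618, and add: *Patients unblinded to placebo keep the option to cross over to DCC-2618 150 mg QD (Section 5.2.2) regardless of any blinded dose reduction.*

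The cost is a change to one clause and one added sentence in a protocol amendment, with a short clarification to sites. No patients, visits or data are added, and no analysis changes.

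### After one dose reduction, the Protocol 5.3.2 text sets no minimum time before return to the starting dose, while Tables 9, 10 and 11 set at least one cycle for the events they cover

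*Protocol*

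**What the plan says.** The relevant material all stands in Protocol 5.3.2.

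**Text.** Interruption and reduction are placed "at the discretion of the Investigator at any time due to AEs and according to the guidelines described in" Tables 8, 9 and 10. Below the reduction ladders (Tables 7 and 8), the text permits re-escalation once the event has recovered, and adds: "Efforts must be made to re-escalate the patient to the dose level at which the AE occurred". For a patient reduced once, the stated condition is that "the AE returns to Grade 1 or baseline, the patient may be re-started at the starting dose level". For a patient reduced twice in sequence, recovery permits a return to the first reduced level, where the patient "must remain at this dose level for 1 cycle without interruption before escalating to the starting dose level".

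**Table 9** (dermatologic toxicity, arthralgia/myalgia), Grade 2 and Grade 3 rows. The condition is: "If after a dose reduction the event is maintained at Grade 1 or baseline for at least 1 cycle (28 days) of dosing". When it is met, the site may think about going up by one level.

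**Table 10** (hypertension), footnote: re-escalation is permitted, at the investigator's discretion, once blood pressure has stayed controlled for at least one full 28-day cycle.

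**Table 11** (other treatment-related events), row for any Grade 3 or 4 event: "Once the AE returns to Grade 1 or baseline, reduce study drug by 1 dose level". On going back up, the same row says: "If a patient tolerates the reduced dose without recurrence of the event for at least one cycle, consider re-escalating the dose of study drug". The step meant is a return to the previous level.

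**The concern.** The text and the tables give different earliest times for the same decision. A site that follows the text can put a patient back on the dose at which the event occurred as soon as the event has recovered. A site that follows the tables would not consider this until at least a cycle had passed. The instruction concerns re-exposure after toxicity, so the first thing at stake is patient safety and consistent handling across sites.

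The analysis is touched only in a secondary way. The timing of re-escalation enters average daily dose and relative dose intensity (SAP 10.1), and an event that recurs after re-escalation could enter the table of adverse events leading to dose modification (SAP 10.2). These summaries are descriptive, and the documents give no basis for putting a size on the effect.

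**Working it through.** No sample size, power or alpha figure is involved, and the plan gives no figure of its own to reproduce. The check sets the rules side by side. The only numerical input is the cycle length of 28 days (Protocol 5.2; also written into Table 9 and the Table 10 footnote).

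**Step 1. Condition for re-escalation after one reduction**

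| Source | Condition | Minimum time |
|---|---|---|
| 5.3.2 text | Event back to Grade 1 or baseline | 0 days |
| Table 9, Grade 2 and 3 rows | Event held at Grade 1 or baseline for at least 1 cycle of dosing after the reduction | at least 28 days |
| Table 10, footnote | Blood pressure controlled for at least 1 full cycle | at least 28 days |
| Table 11, any Grade 3 or 4 | Reduced dose tolerated without recurrence for at least 1 cycle | at least 1 × 28 = 28 days |

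The difference in the minimum is 28 − 0 = 28 days. Because the tables say at least one cycle, 28 days is a floor for the wait under the tables and not a cap.

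**Step 2. Can the text be read as including the wait?** The sentence that follows it imposes one uninterrupted cycle, but only after two sequential reductions. A reader would reasonably take its absence after one reduction as deliberate.

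**Step 3. Do the rules meet on the same patient?** They do.
- Table 9, Grade 3: interruption is for at least 7 days or until recovery, so dosing may resume at a reduced level before the event has recovered. When it then recovers, the text permits the starting dose at once; Table 9 counts a cycle first.
- Table 10, Grade 3: the dose is reduced because blood pressure is not controlled. When the event has returned to Grade 1 or baseline, the text permits the starting dose at once; the footnote counts a full cycle of control.
- Table 11: recovery is the point at which the dose is reduced. The text attaches permission to re-escalate to that same recovery, so read literally it can undo the reduction just made.

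**Step 4. Which reductions are outside the conflict?** The asymptomatic and clinically significant laboratory rows of Table 11 follow other rules and set no one-cycle condition. Table 11 covers treatment-related events only. Sections 5.3 and 5.3.2 also allow discretionary reduction for any adverse event. For a Grade 2 event outside Tables 9 and 10, or an unrelated event outside them, only the text applies.

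**Step 5. Two sequential reductions.** By the text, the minimum is 0 days at the second reduced level plus 28 at the first, so 28 days. If the one-cycle condition of Tables 9 and 11 is applied to each one-level step, which is an assumption, it is 2 × 28 = 56 days. The same mismatch appears here, but the point does not depend on it.

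**The case against.** **The passages can be read together.** The text says the patient may be restarted, Tables 9 and 11 say re-escalation is to be considered, and all three tables are presented as guidance. A site that waits a cycle does not breach the permissive sentence, and a general permission with toxicity-specific timing is a plausible reading. This stands in part: the tables make a cycle the precondition for considering re-escalation and do not order it. It does not remove the conflict. Discretion covers whether to re-escalate, whereas the disagreement is over when that becomes permissible. No precedence is stated, and the text also says that "Efforts must be made to re-escalate the patient to the dose level at which the AE occurred", which pulls towards the earlier time.

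**The sequences differ.** The text has the dose reduced and the event then recovering; Table 11 has the event recover off drug and dosing then resume lower. This has some force for Table 11 if the one-reduction sentence is read alone. However, the general sentence before it permits re-escalation on recovery without regard to sequence, and Table 9 (Grade 3) and Table 10 contain the text's own sequence.

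**Sponsor contact limits divergence.** Protocol 6.11.8 asks that every effort be made to discuss dosing changes with the sponsor beforehand, or failing that to inform the sponsor the same day. This lowers the chance that sites differ in practice. It does not tell the sponsor's representative which of the two conditions to apply.

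**The missing Table 11 is a slip.** This is correct. A reader might infer that sites have no rule for other treatment-related events, but Table 11's title states its own scope, so they do. What remains is a wrong cross-reference that makes the standing of Table 11 less clear.

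**Conclusion.** The contradiction is real and limited. For reductions made under the Table 9 Grade 2 and 3 rows, under Table 10, or under the Table 11 row for any Grade 3 or 4 event, the minimum time before return to the starting dose after one reduction is 0 days by the text and at least 28 days by the tables. This rests on a 28-day cycle and on taking both the text and the tables as current instructions, since the section ranks neither above the other. The number of patients concerned is not given.

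Three stronger readings are not supported:
- A reader might infer that every patient with one reduction is affected. Step 4 of the working shows reductions to which no one-cycle condition applies.
- A reader might infer that the two rules differ by at most 28 days. The tables set a minimum, so the actual difference may be longer.
- A reader might infer harm to the primary analysis. Nothing in the documents shows this, and sample size, power and alpha do not depend on the point.

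It remains worth correcting because it is a safety instruction that sites must apply as written.

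**What to change.** The sponsor should:
1. reconcile the re-escalation paragraph of Protocol 5.3.2 with Tables 9, 10 and 11, so that a given event and grade leads to one condition;
2. state whether the text or the tables govern where both apply, and which rule holds for reductions outside the table rows;
3. say from what point any waiting period is counted, and whether it applies to each step after two reductions;
4. correct the governing sentence so that it refers to Table 11, and check whether the reference to Table 8, which lists reduction steps after escalation to 150 mg BID, is the one intended.

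Which condition is right is for the sponsor to decide; none is proposed here. The cost is clarification wording in the protocol and notice to sites. No endpoint, analysis method or sample size needs to change.
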